10.3 Analysis of Efficacy Variables and Statistical Evaluation

10.3.1 Efficacy Variables

Data such as subjective knee function of each category will presented using criteria for the IKDC, the Lysholm score and the KOOS assessment, and the improvement level of pain will be analyzed using the 100-mm VAS. Structural information will be gained through the use of high-resolution (1.5 or 3 Tesla) magnetic resonance imaging (MRI) with cartilage-specific sequences (T2-mapping).

✓ Primary efficacy endpoint: post-operative change in subjective knee function will be obtained from the IKDC score at the 12-month time point as the primary

CONFIDENTIAL: These all contents herein are the sole property of MEDIPOST Co., Ltd. Any reproduction or distribution of this document without the written consent of MEDIPOST Co., Ltd is prohibited. Copyright © 2017 MEDIPOST Co., Ltd

efficacy endpoint.

- ✓ Secondary efficacy endpoint: the Lysholm Score and the KOOS score will be used as the secondary efficacy endpoint to measure post-operative change of the knee function.
- ✓ Improvement degree of joint pain will be measured using a 100-mm VAS (Visual Analogue Scale).
- ✓ Grade of the cartilage regeneration and morphological constitution of the cartilage repair area will be assessed using high-resolution (1.5 or 3 Tesla) magnetic resonance imaging (MRI).

10.3.2 Analysis of Efficacy Endpoints

The descriptive statistics of the categorical variables will be presented with percentage and frequency and that of the continuous variables such as mean, median, standard deviation, and interquartile range. The primary efficacy endpoint will be analyzed using the t-test. As for the secondary efficacy endpoints, differences of the continuous variables and the categorical variables between the two groups will be analyzed using the t-test and Fisher's exact test, respectively.

CONFIDENTIAL: These all contents herein are the sole property of MEDIPOST Co., Ltd. Any reproduction or distribution of this document without the written consent of MEDIPOST Co., Ltd is prohibited. Copyright © 2017 MEDIPOST Co., Ltd

11 Rehabilitation Protocol

All patients must participate in the following standardized rehabilitation program after receiving treatment. Rehabilitation program will vary according to the defect location of each subject.

Stage 1- Proliferative Phase (Week 1 to 6)

Femoral Condyle Defect

	PRIMARY GOALS
	DO NOT OVERLOAD GRAFT
	INCREASE TIBIOFEMORAL AND PATELLOFEMORAL MOBILITY
	RESTORE QUADRICEPS CONTROL
BRACE	• Knee immobilizer with ambulation, until good quads control/SLR (approximately Week 3 to 6)
GAIT	Heel-toe TDWB with crutches
ROM	• Full AROM and gentle AAROM.
	 CPM ≥ 6 to 8 hours daily for 6 weeks. Start at 0-40 degrees, progress range as tolerated.
	• Goal: minimum 90 degrees flexion for the first 2 weeks, 110 degrees for the next 4 weeks (the 6 week time point of post-op)
THEREX	• Quad sets, SLR in knee immobilizer as needed, leg curl/heel slides, hip abduction
	 Stationary bicycle with no resistance once 90 degrees knee flexion obtained (~ 4 weeks).
	 90 degree leg dangle hourly to improve ROM
THERAPY	 Gentle multi-directional patella mobilization starts immediately after surgery. Cryotherapy and compression stockings/TEDS for swelling and pain control. E-stim for VMO/quadriceps muscle re-education/biofeedback encouraged
	early after surgery if needed.
	 Gentle massage/deep friction to hamstring insertions, suprapatellar quadriceps, medial/lateral gutters, and infrapatellar fat pad region at 2-3 weeks post-op.
	 Pool therapy recommended 2-3 weeks post-op to enhance motion.
	• Foot merapy recommended 2-5 weeks post-op to emiance motion.

page 44 of 137

Femoral Condyle Defect

PRIMARY GOALS DO NOT OVERLOAD GRAFT INCREASE TIBIOFEMORAL AND PATELLOFEMORAL MOBILITY RESTORE QUADRICEPS CONTROL

BRACE	• Knee brace may be discontinued once independent SLR achieved
GAIT	• Week 7 & 8: 50% weight-bearing, week 9+: full weight-bearing
ROM	 Full AROM and gentle PROM exercises Progress towards full ROM until the 12 week time point.
THEREX	 Low weight (max 10-20lbs.) open-chain leg extension and curl Stationary bicycle with gradual increased tension per level of comfort Continue quad sets, SLR in brace, leg curl and heel slides
	 Strengthen quadriceps, hamstrings, and hip abductors/extensors using ankle weights and/or elastic band resistance through full ROM as tolerated Gentle closed-chain terminal knee extension 0 to 40 degrees (TKE) permitted starting from the nine or ten week time point as tolerated per weight bearing restriction
THERAPY	 Gentle multi-directional patella mobilization Cryotherapy and compression stockings/TEDS for swelling and pain control E-stim for VMO/quadriceps muscle re-education/biofeedback encouraged Gentle massage/deep friction to hamstring insertions, suprapatellar quadriceps, medial/lateral gutters, and infrapatellar fat pad region Pool therapy recommended to enhance motion

page 45 of 137

CONFIDENTIAL: These all contents herein are the sole property of MEDIPOST Co., Ltd. Any reproduction or distribution of this document without the written consent of MEDIPOST Co., Ltd is prohibited. Copyright © 2017 MEDIPOST Co., Lt

-- or for trochlear defects --

Stage 1- Proliferative Phase (Week 0 to 6)

Trochlear Defect

	PRIMARY GOALS DO NOT OVERLOAD GRAFT INCREASE TIBIOFEMORAL AND PATELLOFEMORAL MOBILITY RESTORE QUADRICEPS CONTROL
BRACE	 Bledsoe Hinge knee brace for ambulation (locked) and at night Out of brace for CPM. No brace, but towel/pillow behind heel when lying down
PRECAUTIONS	• Full weightbearing in full extension (locked brace)
ROM	 Gentle AROM flexion as tolerated 3x/day. Only PROM extension allowed. CPM ≥ 6 to 8 hours daily. Starting from 0 to 40 degrees, progress range as tolerated after the first 2 weeks. Minimum 90 degrees flexion for the first 2 weeks, 110 degrees for the next 4 weeks
THEREX	 Quad sets, SLR with brace locked, leg curl/heel slides, hip abduction Stationary bicycle with no resistance once 90 degrees knee flexion obtained (> 4wks). 90 Degree Leg dangle hourly to improve ROM
THERAPY	 Gentle multi-directional patella mobilization right after surgery Cryotherapy and compression stockings/TEDS for swelling and pain control. E-stim for VMO/quadriceps muscle re-education/biofeedback encourage early after surgery if necessary. Gentle massage/deep friction to hamstring insertions, suprapatellar quadriceps, medial/lateral gutters, and infrapatellar fat pad region at the two to three week time point post-op. Pool therapy recommended two to three weeks post-op to enhance motion.

CARTISTEM®

page 46 of 137

CONFIDENTIAL: These all contents herein are the sole property of MEDIPOST Co., Ltd. Any reproduction or distribution of this document without the written consent of MEDIPOST Co., Ltd is prohibited. Copyright © 2017 MEDIPOST Co., Lt

Trochlear Defect

PRIMARY GOALS DO NOT OVERLOAD GRAFT INCREASE TIBIOFEMORAL AND PATELLOFEMORAL MOBILITY **RESTORE QUADRICEPS CONTROL** BRACE Hinged knee brace may be discontinued once independent SLR achieved ٠ GAIT ٠ Full weight-bearing as tolerated ROM Gentle A/AAROM flexion and extension permitted ٠ Progress towards full ROM until week 12. THEREX Stationary bicycling without resistance at short intervals (5 min, 2-3x/day) as ٠ tolerated ٠ Strengthening of quadriceps, hamstrings, and hip abductors/extensors using elastic band isometrics and closed-chain terminal knee extension 0-40 degrees only Backward treadmill walking with safety bars recommended to reduce • patellofemoral compressive forces Pool exercise using kickboard allowed. Flutter/straight leg scissor kick only (no ٠ whip kick) No open-chain strengthening permitted until 6 months after surgery. No closed-chain leg pressing or squatting ٠ THERAPY Gentle multi-directional patella mobilization ٠ Cryotherapy and compression stockings/TEDS for swelling and pain control ٠ E-stim for VMO/quadriceps muscle re-education/biofeedback encouraged ٠ Gentle massage/deep friction to hamstring insertions, suprapatellar quadriceps, ٠ medial/lateral gutters, and infrapatellar fat pad region Pool therapy recommended to enhance motion ٠

page 47 of 137

CONFIDENTIAL: These all contents herein are the sole property of MEDIPOST Co., Ltd. Any reproduction or distribution of this document without the written consent of MEDIPOST Co., Ltd is prohibited. Copyright © 2017 MEDIPOST Co., Ltd

12 References

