CONFIDENTIAL: These all contents herein are the sole property of MEDIPOST Co., Ltd. Any reproduction or distribution of this document without the written consent of MEDIPOST Co., Ltd is prohibited. Copyright © 2017 MEDIPOST Co., Ltd.

	_
	5 cm ² , will be enrolled and treated (Dosage B) to further evaluate safety.
	Efficacy: Efficacy will be evaluated with several validated clinical outcome instruments as primary endpoints as well as non-invasive structural assessment utilizing high-resolution magnetic resonance imaging with cartilage-specific sequences as a secondary endpoint.
Objectives:	
Primary Objective	To evaluate the safety of CARTISTEM [®] administration
Secondary Objectives	To evaluate the exploratory efficacy (improvement in Clinical Scores and regeneration of defective cartilage as assessed by Radiological images) of CARTISTEM [®] .
Diagnosis and Main Criteria for Inclusion	 Patients must meet the following criteria to be eligible for the study; Patients with an intended- to- treat single focal, full-thickness cartilage defect (ICRS [International Cartilage Repair Society] Grade 3 or 4) of the knee as a result of ageing, trauma, or degenerative diseases. Age ≥ 18 years old Size of the articular cartilage lesion is ≥ 2 cm² Swelling, tenderness and active range of motion ≤ Grade II Joint pain : 20-mm - 60-mm on VAS (Visual Analog Scale) at the time of Screening Appropriate blood coagulation, kidney and liver function laboratory parameters: ✓ PT(INR) < 1.5, APTT <1.5×control ✓ Creatinine ≤ 2.0 mg/dL, Albumin ≤ trace in urine dipstick test ✓ Bilirubin ≤ 2.0 mg/dL, AST/ALT ≤ 100 IU/L Ligament instability ≤ Grade II Lower extremity alignment within 5 degrees of the neutral weight bearing axis No meniscal surgery within the past 3 months and more than 5mm of meniscal rim remaining Ability and willingness to fully participate in the post-operative rehabilitation program Subject is informed of the investigational nature of this study, voluntarily agrees to participate in the study, and signs an IRB-approved informed consent prior to performing any of the screening procedures

[figure not shown]
page 3 of 137

CONFIDENTIAL: These all contents herein are the sole property of MEDIPOST Co., Ltd. Any reproduction or distribution of this document without the written consent of MEDIPOST Co., Ltd is prohibited. Copyright © 2017 MEDIPOST Co., Ltd.

	• Body Mass Index (BMI) $\leq 35 \text{ kg/m}^2$

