CONFIDENTIAL: These all contents herein are the sole property of MEDIPOST Co., Ltd. Any reproduction or distribution of this document without the written consent of MEDIPOST Co., Ltd is prohibited. Copyright © 2017 MEDIPOST Co., Ltd.

Clinical Trial Material (CTM)	CARTISTEM [®] (human allogeneic-unrelated umbilical cord blood-derived mesenchymal stem cells, hUCB-MSC, and sodium hyaluronate) CARTISTEM [®] consists of approximately 7.5 x 10 ⁶ hUCB-MSC suspended in 1.5 mL medium in one vial, and 60 mg sodium hyaluronate provided as a lyophilized sponge form in a separate vial. The two vials are mixed at the surgical site. Upon admixture of the two vials, the combination forms a viscous gel, which is implanted into the articular cartilage defect.
Clinical Trial Material Dosage and Administration	CARTISTEM [®] will be administered into the articular cartilage defect by open surgery at a dose of 0.5 mL/cm ² based upon size of the defect. The CARTISTEM [®] dosage has been selected based on the results derived from nonclinical studies and prior human experience (see Investigator's Brochure for further information)
Surgical Technique	Before application of CARTISTEM [®] , unstable chondral fragments are debrided using a curet and stable shoulders of healthy surrounding cartilage are created. After adequate removal of the debris, multiple holes are created across the entire articular cartilage defect with a 2~3 mm drill bit spacing the holes approximately 3~5 mm apart. CARTISTEM [®] is applied onto the drilled holes first, and then throughout the entire cartilage defect.
Post-operative rehabilitation	Patients will be started on a continuous passive motion (CPM) device on post-operative day 1 with a range of motion of 0-30 degrees initially. This will be increased by 10 degrees per day as tolerated to a maximum of 0-90 degrees. Patients will undergo CPM treatment for 6 hours per day over 6 weeks. The patient will remain touch-down weight-bearing (TDWB) for 6 weeks, and then advance to full-weight bearing during the next 6 weeks (up to week 12). The patient will refrain from high-impact activities, such as running, during the subsequent 8 to 12 weeks (week $20 - 24$).
Reference Therapy	The study does not include a reference compound.

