Efficacy Evaluation	Primary efficacy outcome parameters will be the postoperative changes in subjective knee function as assessed by IKDC (International Knee Documentation Committee) score at 12 months. For secondary efficacy outcome parameters, patients will answer questionnaires for pain (visual analogue scale, VAS), knee specific outcome instruments (Lysholm knee scoring, and KOOS [Knee injury and Osteoarthritis Outcome Score]). Structural information will be gathered using high-resolution (1.5 or 3 Tesla) magnetic resonance imaging (MRI).

page 7 of 137

CONFIDENTIAL: These all contents herein are the sole property of MEDIPOST Co., Ltd. Any reproduction or distribution of this document without the written consent of MEDIPOST Co., Ltd is prohibited. Copyright © 2017 MEDIPOST Co., Ltd.

Statistical Methods	General: all safety and efficacy endpoints will be presented for each dose cohort as well as for all patients combined. For safety evaluation, statistical homogeneity between dose groups will be performed. For efficacy evaluation, statistical comparison (difference) between dose groups will be performed.
	1) Safety Safety will be demonstrated with 95% confidence intervals. Adverse events, adverse drug reactions, serious adverse events, and drop-out patients due to AE will be presented with frequency and percentage. Homogeneity between dose groups will be analyzed using person's chi-square test or Fisher's exact test. Descriptive statistics including means, medians, SD (standard deviation), minimum and maximum will be used to demonstrate the other safety endpoints.
	2) Efficacy Symptom improvement from the outcome instruments will be demonstrated with means and standard deviations. Efficacy results will also be analyzed for statistical significance using change from baseline at each efficacy endpoint. Statistical difference of continuous variables and categorical variables between dose groups will be compared using t-test and Fisher's exact test, respectively.
Rationale for Study Population and Number of Patients	CARTISTEM [®] is administered to the defective joint cartilage region by open surgery. Due to ethical considerations, it is not possible to conduct this type of procedure in a healthy subject. Therefore, no studies in healthy subjects will be performed.

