Support for the range of CARTISTEM[®] doses (0.5×10^7 cells to 2.25×10^7 cells) to be evaluated for safety and efficacy in this phase I/IIa study comes from both preclinical studies and clinical results in humans (comprised of a completed Phase I/II study in Korean patients with articular cartilage defects (N=7) and an ongoing Phase III study in Korean patients (N=50), as follows:

NOAELs for CARTISTEM[®] have been determined in the rat (Study No. B04001; NOAEL = $3x10^7$ cells per mL; > $1x10^7$ cells per cm²) and the rabbit (Study No. B04004; NOAEL = $1.5x10^7$ cells per mL; > $0.3x10^7$ cells per cm²); however, it is possible that the design of these studies did not allow for a proper assessment of the NOAEL due to limitations on the density of cells administered, and an overall very low toxicity of the hUCB-MSC in the species examined.

No treatment-related SAEs have been reported in seven patients who participated in a phase I/II Korean study and 50 patients currently enrolled in an ongoing phase III Korean study; all of these patients have received single administrations of 0.25×10^7 cells/cm² (0.5 ml/cm² with $0.5x10^7$ MSC/mL) up to a maximum of $2.25x10^7$ total MSC; this number of cells represents a much higher dose than the NOAEL ($10x10^7$ MSC per mL) derived from CARTISTEM® page 22 of 137

CONFIDENTIAL: These all contents herein are the sole property of MEDIPOST Co., Ltd. Any reproduction or distribution of this document without the written consent of MEDIPOST Co., Ltd is prohibited. Copyright © 2017 MEDIPOST Co., Ltd.

Study B04001 (GLP repeat-dose toxicology study in rats).

Based on these findings (for further discussion, please see the Investigator's Brochure), MEDIPOST has selected a single administration of CARTISTEM[®] at 0.25×10^7 cells/cm² (0.5 mL/cm² with 0.5×10^7 hUCB-MSC/mL), with both the volume and total number of hUCB-MSC administered to patients being a function of the defect size.

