10.1.2 Efficacy Population

The efficacy population will be defined as all patients who met the eligibility criteria and received at least one dose of the investigational product, and had been assessed at least once for at least one efficacy endpoint.

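### Does it matter that Section 10.3.2 does not say which t-test applies to the 12-month change in IKDC?

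*Combined protocol and SAP*

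**What the plan says.** Section 10.3.1 sets the primary efficacy endpoint: "post-operative change in subjective knee function will be obtained from the IKDC score at the 12-month time point as the primary" efficacy endpoint. Section 10.3.2 then gives the method in one sentence: "The primary efficacy endpoint will be analyzed using the t-test". It names no groups, null value, significance level or confidence interval. The following sentence, which is limited to the secondary endpoints, specifies a comparison between the two groups.

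The synopsis (Statistical Methods, Efficacy) has two further statements. One concerns change over time: "Efficacy results will also be analyzed for statistical significance using change from baseline at each efficacy endpoint". The other concerns cohorts: "Statistical difference of continuous variables and categorical variables between dose groups will be compared using t-test". Its general paragraph asks for every safety and efficacy endpoint to be shown by dose cohort and for all patients combined, and adds that efficacy will be compared between dose groups.

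The cohorts are defined by lesion size (2 to 5 cm² and above 5 cm²) and enrolled in sequence. All patients receive the same number of cells per cm², "with both the volume and total number of hUCB-MSC administered to patients being a function of the defect size" (dosage rationale, Section 6). There is no control arm: "The study does not include a reference compound".

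**The concern.** Wherever the plan gives an efficacy t-test a stated contrast, that contrast is Dosage A against Dosage B. If the same is meant for the primary endpoint, the headline efficacy test would not measure improvement, which is what the efficacy objective asks about. It would measure a difference between cohorts in which total cell dose cannot be separated from lesion size, and is closely tied to enrolment order. The change-from-baseline analysis has no named test, 10.3.2 does not repeat it, and confidence intervals are specified only for safety.

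At stake is the meaning of the primary efficacy result. The same data could be presented as clear improvement or as a null finding, depending on a choice that the plan does not state and that could be made after open-label results are known.

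Two smaller points add to the impression of looseness. The Study Overview says "Efficacy will be evaluated with several validated clinical outcome instruments as primary endpoints", although IKDC is the single primary efficacy endpoint elsewhere. The efficacy population admits anyone who "received at least one dose of the investigational product, and had been assessed at least once for at least one efficacy endpoint", so a member may lack a 12-month IKDC value.

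**Working it through.** **Inputs.** Cohort sizes are 6 to 9 per cohort, 12 to 18 in total (Section 6.3). The plan gives no efficacy alpha, sidedness, effect size or SD, and Section 6.3 says the sample size is not based on a power calculation. There is therefore no figure of the plan's own to reproduce. Assumptions: two-sided 5%, effects in units of the SD of 12-month IKDC change, and the same SD in both cohorts.

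**How far apart the two readings are.**

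95% CI half-width for A minus B is t(0.975, 2n−2) × √(2/n):
- 6 vs 6: 2.228 × √(2/6) = 1.29 SD
- 9 vs 9: 2.120 × √(2/9) = 1.00 SD

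95% CI half-width for mean within-patient change, cohorts combined, is t(0.975, N−1) / √N:
- N = 12: 2.201 / √12 = 0.64 SD
- N = 18: 2.110 / √18 = 0.50 SD

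If the SD were 10 to 20 IKDC points (an assumption), these are 12.9 to 25.7 points for A minus B at 6 vs 6, and 6.4 to 12.7 points for overall change at N = 12.

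Rejection probabilities from the noncentral t distribution:
- Both cohorts improve by 1 SD. Paired, N = 12, noncentrality 1 × √12 = 3.46: 0.88. A versus B, noncentrality 0: 0.05, which is simply the assumed alpha.
- Cohorts differ by 1 SD. A versus B at 6 vs 6, noncentrality 1 × √(6/2) = 1.73: 0.35. At 9 vs 9: 0.51.

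The readings are thus far apart. The remaining question is whether the plan leaves the improvement result out.

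**What the text supports, side by side.**

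| Place | Improvement from baseline | A versus B |
|---|---|---|
| 10.3.1 | Endpoint is a post-operative change | – |
| 10.3.2, primary | t-test on that change; no groups named | Not stated |
| 10.3.2, secondary | – | Stated |
| Synopsis, Efficacy | Significance of change from baseline | t-test between dose groups |
| Synopsis, General | Results for all patients combined | Results by cohort; comparison between groups |

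Both analyses are in the plan. For the primary endpoint, a t-test on a change score with no groups named is most simply a paired (one-sample) test. That reading also supplies the test missing from the synopsis sentence on change from baseline.

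**Whether an unnamed interval loses anything.** The synopsis and 10.3.2 call for means and SDs. With the number of patients, the interval for change is mean ± t × SD/√N. The interval for A minus B follows in the same way from the cohort means and SDs. Neither needs data beyond what is already to be reported.

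**Whether anything depends on the choice.** Escalation, halting and the maximum tolerated dose (Sections 6.5 and 6.6) use dose-limiting toxicity only. No efficacy success criterion is stated, and no efficacy dose-response claim is made.

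**The case for a change.** The best case for a change is that exploratory status does not excuse leaving the analysis of a designated primary efficacy endpoint open. The synopsis promises a significance analysis, the trial is open-label, and the choice of contrast could follow the data. The synopsis's general sentence on comparing dose groups does lean towards the A-versus-B reading, and defining the endpoint as a change does not exclude it, since changes can also be compared between cohorts. One added word would settle the matter.

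Most of that is right as a description of the text: the wording is ambiguous, and the gap between 0.88 and 0.05 shows that the two tests are not interchangeable. What does not stand is the inference that one result would replace the other. The synopsis calls for both, with pooled and by-cohort displays, so choosing a label after the fact could not remove the improvement result from a report that follows the plan.

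The confounding of total dose with lesion size comes from the design, is set out openly in the dosage rationale, and is the same however the test is named. Likewise, the lack of a control arm means that change cannot be credited to the product rather than to debridement, drilling or rehabilitation, under either reading.

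**Conclusion.** The ambiguity exists, but it is missing detail that a competent analyst fills sensibly: a paired test on the 12-month IKDC change, with A minus B reported as a comparison of defect-size cohorts. The quantities involved (half-widths of 0.64 SD for overall change at 12 patients and 1.29 SD for A minus B at 6 vs 6) come from the small sample and would be the same after any rewording. They rest on an assumed two-sided 5% level and a common SD.

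The side points are of the same kind. The plural primary endpoints in the Study Overview are a clerical slip: the synopsis's Efficacy Evaluation and Sections 8.4.6 and 10.3.1 all agree on IKDC at 12 months. A patient without both IKDC values cannot contribute a change score, and with 12 to 18 patients the number who do is plain from the table. Safety is the primary objective, efficacy is exploratory, and no decision uses this p-value. Extra wording would record what the plan already leads to without altering a result, so no change is called for.

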6.3 Number of Subjects

1) Estimated Number of Patients

This study requires 12-18 patients (6-9 patients per arm depending on rate of DLT) for two different dose ranges (Dosage A: defect sizes of 2-5 cm² and Dosage B: defect sizes of above 5 cm²).

2) Target Number of Subjects and Rationale

This is a phase I/IIa clinical trial to evaluate safety and exploratory efficacy of the investigational drug product. Therefore, it is not considered critical to base the number of subjects on formal statistical power calculations. Six patients at each dose cohort enrolled sequentially are considered sufficient for this study. This study will be performed with two dose ranges, on the basis of existing pre-clinical test results. Initially, 6 patients with defect sizes of 2-5 cm² will be enrolled in Dosage A. If no DLT is seen during Dosage A, another 6 patients with larger defect sizes (above 5 cm²) will be recruited for Dosage B of the study. There could be a need for an intermediate dose or up to 6 additional patients, based on the rate of DLT seen.

CARTISTEM®

page 21 of 137

CONFIDENTIAL: These all contents herein are the sole property of MEDIPOST Co., Ltd. Any reproduction or distribution of this document without the written consent of MEDIPOST Co., Ltd is prohibited. Copyright © 2017 MEDIPOST Co., Ltd.

1) Initial Administration Dosage and Rationale

It is somewhat well understood by developers and regulators of living cell therapies that for products like CARTISTEM[®] administered locally into an anatomical defect there is no simple extrapolation of a safe starting dose in humans based primarily upon body surface area calculations derived from animal studies.

In addition, dose determinations in this clinical setting should take into account the surface area of the cartilage defect such that all NOAEL values should be converted into a unit quantity (cells/cm²) at the application site. This approach applies to most therapeutics administered into anatomical compartments that have little subsequent distribution outside of the compartment; it is recommended that doses are normalized between species according to the compartmental volumes and amount of the therapeutic product.

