8.5 Early Discontinuation from the Study

Drop-out or withdrawal of a subject from the study can be determined at any time point during the study period by reporting to the trial coordinator or the principal investigator.
CARTISTEM® page 39 of 137

CONFIDENTIAL: These all contents herein are the sole property of MEDIPOST Co., Ltd. Any reproduction or distribution of this document without the written consent of MEDIPOST Co., Ltd is prohibited. Copyright © 2017 MEDIPOST Co., Ltd

Should a patient voluntarily decide to withdraw, the decision will be respected and accepted without any questions.

Purpose of this study is to evaluate the safety and the efficacy of the investigational product. Therefore, any subjects who want to withdraw from the study on a voluntary basis or due to the adverse events will be replaced with new subjects as long as the drug administration in the dosage group that the withdrawn subject was in is not complete. The study data obtained from such a subject until the point of drop out will be, where possible, included in the data pool for analysis at the final evaluation stage.

9 Definition of Adverse Events

An adverse event (AE) is defined as any undesired clinical responses or complication experienced by a subject. All operative and postoperative adverse events, whether related or not, will be documented on the AE case report form (CRF).

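### Fisher's exact test ignores order, so if the MRI regeneration grade has three or more ordered levels, section 10.3.2 and the synopsis should name an exact rank test for it

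*Combined protocol and SAP*

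**What the plan says.** For efficacy endpoints other than the primary one, section 10.3.2 gives a single rule: "differences of the continuous variables and the categorical variables between the two groups will be analyzed using the t-test and Fisher's exact test, respectively". The synopsis, under Statistical Methods, repeats it: "Statistical difference of continuous variables and categorical variables between dose groups will be compared using t-test and Fisher's exact test, respectively". Neither place names a rank, trend or other ordinal method.

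Section 10.3.1 lists the efficacy variables. IKDC, Lysholm, KOOS and the 100-mm VAS yield numeric scores. The MRI item is worded differently: "Grade of the cartilage regeneration and morphological constitution of the cartilage repair area will be assessed using high-resolution" MRI. No grading instrument, number of levels or ordering is given there or in section 8.4.10, and no sentence assigns the MRI item to either test.

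Section 6.3 plans 6 patients per cohort, rising to as many as 9 if dose-limiting toxicity occurs. It says of the sample size that "it is not considered critical to base the number of subjects on formal statistical power calculations". The plan states no alpha or effect size for any efficacy comparison.

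**The concern.** Regeneration of the defective cartilage is part of the secondary objective (synopsis and section 5), and the MRI grade is its most direct listed readout. A grade of regeneration would ordinarily run from worse to better. Fisher's exact test on a 2 x k table treats the grades as unordered labels, so its p-value does not change when the grades are shuffled. It asks whether the two distributions differ in any way, not whether one cohort regenerated more cartilage.

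Two errors follow with 6 to 9 patients per cohort. A clear ordered shift can go undetected, and a difference with no better or worse direction can be reported as significant.

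**Working it through.** **Nothing to reproduce.** The plan gives no power figure for this comparison. The check therefore compares the stated test with an exact rank test.

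**Inputs.** From the documents: 6 v 6 (up to 9 v 9), and Fisher's test for categorical variables. Assumed, because not stated: two-sided 5% level, 3 to 5 grades, the spread of the grades, and a proportional-odds shift between cohorts.

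**Step 1: two worked tables, 6 v 6, four grades, three patients in each grade overall.** The number of allocations is C(12,6) = 924. A table with cohort A counts (a1, a2, a3, a4) has weight C(3,a1) x C(3,a2) x C(3,a3) x C(3,a4). Over all tables the weights total:

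- weight 1: 6 tables, total 6
- weight 9: 24 tables, total 216
- weight 27: 8 tables, total 216
- weight 81: 6 tables, total 486

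The sum is 924. Fisher's p adds the weights no larger than the observed one. For the rank test, scoring the grades 0 to 3 is equivalent to mid-ranks here. Cohort A's score sum S has expectation 9, and p adds the weights at least as far from 9 as observed.

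*Clear shift:* A (3,2,1,0) v B (0,1,2,3), counts from low to high grade.
- Fisher: the observed weight is 9, so p = (6 + 216)/924 = 0.240.
- Wilcoxon: S = 4, distance 5. Only S = 4 (weight 9) and S = 3 (weight 1) are as extreme on that side, so p = 2 x (9 + 1)/924 = 0.022.
- Probability that a B patient has the better grade, ties counted half: of 36 pairs, B is better in 31, tied in 4 and worse in 1, giving (31 + 2)/36 = 0.92.

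*No shift:* A (0,3,3,0) v B (3,0,0,3).
- Fisher: the observed weight is 1, so p = 6/924 = 0.0065.
- Wilcoxon: S = 9, distance 0, p = 1.0. The probability of a better grade is 18/36 = 0.50.

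**Step 2: power.** Power is the sum, over all pairs of count vectors, of the two multinomial probabilities wherever the exact conditional p-value is at most 0.05. The cumulative logits of the two cohorts are shifted by plus and minus ln(OR)/2 about evenly spread grades. Results at 6 v 6, in percent (Fisher / exact Wilcoxon / gain in points):

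| Grades | OR 5 | OR 10 | OR 20 |
|---|---|---|---|
| 3 | 14.4 / 18.5 / 4.1 | 29.7 / 36.7 / 7.0 | 49.1 / 56.9 / 7.8 |
| 4 | 14.4 / 22.4 / 8.0 | 29.7 / 42.7 / 13.0 | 49.8 / 63.9 / 14.1 |
| 5 | 14.1 / 24.6 / 10.5 | 28.8 / 45.6 / 16.8 | 48.9 / 66.8 / 17.9 |

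At OR 3 the gain is about 2 to 5 points (4 grades: 7.6 v 11.6; 5 grades: 7.7 v 13.0). At 9 v 9 with 4 grades and OR 10 the figures are 52.9 v 67.3. With no shift, both tests reject in 2.2% to 3.4% of cases at 6 v 6, so the gain does not come from inflated error.

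**Step 3: sensitivity to the assumptions.** Here one cohort is held at a stated distribution (even, or skewed towards low grades) and the other is shifted, with ORs from 2 to 40. The 6 v 6 gains are 0.5 to 6.1 points with 3 grades, 1.4 to 15.3 with 4, and 1.9 to 24.6 with 5. The largest has one cohort at 35/25/20/15/5% and OR 20: 40.5 v 65.1. With one cohort evenly spread over 5 grades, the OR 10 gain falls to 10.0 points (28.1 v 38.1). With two grades the tests coincide and the gain is zero.

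**The case against.** The strongest objection is that the premise is inferred. The plan does not say that the MRI grade is ordered or categorical. The imaging includes T2-mapping, so the readout could be a numeric measure or a summed score, which 10.3.2 already sends to the t-test. The morphology item may be nominal, and Fisher's test suits it. This stands: the point is conditional, and defining the scale comes first.

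A reader might also infer a definite loss, such as 8 to 17 points. The documents give no scale, effect size or alpha that would support it. In the step 3 grid of 42 shift scenarios at 6 v 6, 10 fall in that band, 28 are below 8 and 4 are above 17.

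The stakes are low, and this also stands. The cohorts are enrolled in sequence and defined by defect size, so any difference in regeneration is confounded with lesion size. Escalation in section 6.5 rests on dose-limiting toxicity, not on this p-value. The rank test itself reaches only 11.6% power at OR 3 and 22.4% at OR 5 with 4 grades. The no-shift table is an extreme case, chosen to show what Fisher's test responds to. None of this makes Fisher's test the better choice for ordered grades in a comparison the plan has committed to making.

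Finally, a reader might extend the argument to a signed-rank test on change in grade from baseline. The documents define no pre-treatment value for a regeneration grade, and that test also needs comparable spacing between grades. It is not recommended here.

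**Conclusion.** The point holds conditionally and is minor. If the MRI grade has three or more ordered levels and is handled as categorical, the stated test ignores direction and loses power for a directional shift. At 6 v 6 the loss is under 1 to about 25 points across the assumed scenarios. With grades evenly spread on average over the two cohorts, it is about 2 to 5 points at OR 3 and 7 to 17 points at OR 10. These figures rest on 3 to 5 grades, proportional odds and exact two-sided 5% tests, none of which the plan states. The insensitivity to order does not depend on those assumptions; the size of the loss does.

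**What to change.** In section 10.3.2 and the synopsis:

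1. State the MRI grading scale, its levels and their order.
2. Specify that ordered categorical endpoints are compared between cohorts with the exact Wilcoxon-Mann-Whitney test on the full grades, using mid-ranks for ties. Report the probability that a patient in one cohort has a better grade than a patient in the other, with its 95% confidence interval.
3. Keep Fisher's exact test for unordered or binary variables, including any nominal description of repair morphology.

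The cost is a few sentences; the same MRI readings are used, with no extra patients or visits. The one loss is sensitivity to non-monotone patterns, which do not bear on whether regeneration is better or worse. The wording should be settled before the grades are read.
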